1. INTRODUCTION

1.1 General Introduction

Dental implants have become an important and popular treatment option to replace absent or lost teeth. It is expected that implant prevalence could reach as high as 23% of US adult population by 2026 based on current NHANES data trends (Elani et al. 2018). The survival rate of dental implants is as high as 96.8% for 5 years and 92.8% for 10 years (Jung et al. 2007). Over time, the reported survival rates for all types of implant restorations have continued to increase, however, the incidences of esthetic, biologic, and technical complications are still high (Pjetursson et al. 2014). If untreated, complications associated with implant dentistry may result in progressive inflammation, bone loss, and ultimately, implant failure. Peri-implant mucositis is defined as inflammation in the peri-implant mucosa without peri-implant bone loss (Heitz-Mayfeild & Salvi, 2018). Clinical signs of inflammation of the peri-implant mucosa include bleeding on probing, erythema, swelling, and suppuration (Heitz-Mayfeild & Salvi, 2018). Peri-implantitis is defined as a pathological condition around implant tissues with inflammation and progressive loss of supporting bone around the implant (Schwarz et al. 2018). Clinically, peri-implantitis includes the presence of inflammation, radiographic bone loss, and increasing probing depth (Renvert et al. 2018). The etiology of peri-implant mucositis and peri-implantitis is through the development and accumulation of a bacteria biofilm around the implant. Peri-implant disease etiology is similar to the etiology of gingivitis and periodontitis. Disease is caused by the host response to a bacterial biofilm with a shift in bacterial species and type as the disease progresses. Biofilm-induced peri-implant mucositis is reversible by the removal of plaque from around the implant (Salvi et al. 2011). It is important to treat peri-mucositis professionally through mechanical removal of bacteria biofilm, preventing disease progression to peri-implantitis and prevent implant loss (Schwarz et al, 2015). The gold standard of care in the treatment of inflammation of implants is the mechanical removal of plaque with the use of curettes and ultrasonics. Conventional mechanical debridement of the implant surface is limited by the contaminated microstructure of the implant surface. Bacteria might be protected by residing in micro-irregularities of the titanium implant surface. Therefore, antimicrobial adjuncts have been advocated to increase the range of effective treatment in reducing inflammation around implants over the usual standard of mechanical debridement (Figuero et al. 2014). Options of adjuncts in the treatment of peri-implant inflammation include systemic antibiotics, local antibiotics, and antiseptics. Laser therapy such as antimicrobial photodynamic therapy (aPDT) can be used as an adjunct in the treatment of peri-implant mucositis and peri-implantitis. Antimicrobial photodynamic therapy uses low level laser light and aims to destroy pathogens around the implant and can also act as a photobiomodulator reducing inflammation and stimulating cellular proliferation (Mizutani et al. 2016). The advantages of aPDT are its wide antimicrobial activity, can be applied multiple times without creating antibiotic resistance, and easier topical delivery reaching the micro-irregularities of the implant surface.

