2.2 Primary Outcome Measures

This study aims to compare clinical outcomes (change in BOP and PPD) after mechanical debridement of implant surfaces at sites exhibiting plaque induced inflammation with or without adjunctive aPDT. Bleeding on probing and periodontal probing depths will be assessed clinically through a periodontal probing exam at baseline, week 6, and week 12 follow up. Probing depth reduction endpoint value of 1mm (Bassetti et al. 2014, Morrison et al. 1980). Bleeding on probing endpoint value of 50-60% reduction of sites with BOP (Bassetti et al. 2014). Demographic and implant related variables will be analysed using multivariate analysis for correlation with peri-implant mucositis and peri-implantitis.

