2.3 Secondary Outcome Measures

In addition to the clinical outcomes, plaque samples and peri-implant sulcular fluid (PISF) will be taken to assess the microbiologic and immunologic profile before and after treatment with or without aPDT. Subgingival biofilm samples will be collected using sterile titanium implant scalers and will be assessed at baseline and week 12 follow up. PISF will be collected from the tested implant site after clinical examination. The levels of interleukin (IL)-1 α , IL-1 β , IL-6, IL-8, IL-10, IL-12, IL-7A, tumor necrosis factor (TNF)- α , C-reactive protein, osteoprotegerin, leptin, and adiponectin will be determined using multiplex proteomic immunoassays.

2.4 Potential Risks and Benefits:

a. End Point – Efficacy

All eligible patients needing non-surgical treatment of peri-implant disease will receive the appropriate treatment of mechanical debridement. The mechanical removal of plaque around the implants is the gold standard of care in the treatment of implant inflammation. The patients in the adjunctive aPDT group may have improved healing as observed through surrogate clinical measures of inflammation (BOP, PPD), greater microbiologic reduction, and levels of key biomarkers in PISF that resembles peri-implant tissue health (Recker 2015).

b. End Points – Safety

1) Study related risks:

Initial mild pain, swelling, and bleeding related to non-surgical implant surface mechanical debridement. Potential for antimicrobial methylene blue dye to reversibly stain gingiva around implant site. Collecting PISF will not result in any additional side effects. Patient will not be provided medications for study

related pain. If patient reports pain after treatment will recommend over the counter analgesics such as ibuprofen or acetaminophen.

2) Protection against risk:

All efforts will be made to minimize risks to all and every participant. Laser safety protocols will be followed including laser safety mechanisms, labels and signage, safety zone implementation, proper eye protection for patient and clinician.

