reviewed with all patients including techniques to clean around implants. Mechanical debridement of implant surfaces will be completed with titanium scalers and ultrasonics removing supragingival and subgingival plaque. Antimicrobial photodynamic therapy will be done at implant sites by applying a photosensitizing dye methylene blue (0.1 mg/ml) with a disposable syringe from the bottom of pocket in a coronal direction. The methylene blue dye will be diluted from 1.0% to 0.1% before use. The dye will be applied topically confined to the epithelialized space surrounding the implant fixture and will not be internalized. After 5 minutes in situ, the surrounding gingival tissues will be irradiated at six sites around the implant using a diode laser with a wavelength of 660nm, providing an energy density of 10 J/site, 100mW power, time equal to 100 seconds. After irradiation, the site will be thoroughly rinsed with saline. Only pockets \geq 4mm will be treated with the diode laser as this is the threshold pocket for diagnosing peri-implant inflammation per the 2017 World Work Workshop (Heitz-Mayfield & Salvi, 2018).

Clinical Measurements

Implant sites will be evaluated at baseline, six weeks, and twelve weeks after treatment (2 follow-up visits in total). Improvement in sites resulting from a reduction in inflammation will be analyzed based on pocket depth, clinical attachment loss, bleeding on probing, and the presence of plaque. For clinical measurements, six sites around the implant will be measured: mesial buccal, mid buccal, distal buccal, mesial lingual, mid lingual, and distal lingual. Bleeding on probing will be evaluated by gently sweeping the periodontal probe just within the gingival sulcus of the implant and the presence or absence of bleeding will be recorded. The presence or absence of plaque will then be evaluated at six sites around the implant surface. Plaque sampling will be performed prior to the remaining clinical measurements at the baseline/treatment appointment and 12 weeks after treatment utilizing a titanium curette within the gingival sulcus of the inflamed site. Periodontal pocket depth is measured from the free gingival margin to the base of the pocket, with a UNC periodontal probe with 1mm measurement units. Clinical attachment loss is measured by subtracting the pocket depth from distance of the free gingival margin to the implant platform.

Microbiologic collection and analysis

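### Plaque is scored after the bleeding sweep and is then labelled a result of reduced inflammation; score it first and report it as a hygiene check (minor)

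*Combined protocol and SAP*

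**What the plan says.** Section 6.3b, under Clinical Measurements, sets out the readings in order. The bleeding test comes first: "Bleeding on probing will be evaluated by gently sweeping the periodontal probe just within the gingival sulcus of the implant". Next comes the plaque score: "The presence or absence of plaque will then be evaluated at six sites around the implant surface". Where a plaque sample is due (baseline and week 12), it is taken before the remaining measurements.

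The same paragraph says that improvement "resulting from a reduction in inflammation will be analyzed based on pocket depth, clinical attachment loss, bleeding on probing, and the presence of plaque".

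Section 1.1 gives the causal direction as the protocol understands it: "The etiology of peri-implant mucositis and peri-implantitis is through the development and accumulation of a bacteria biofilm around the implant".

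On outcomes, section 2.2 states: "This study aims to compare clinical outcomes (change in BOP and PPD) after mechanical debridement of implant surfaces". Section 2.3 adds that "plaque samples and peri-implant sulcular fluid (PISF) will be taken to assess the microbiologic and immunologic profile"; those are laboratory samples, not the presence/absence score. The hypotheses in sections 2.1 and 5.1 do not mention a plaque score either. Sections 5.1 and 6.1 list plaque only as one of the clinical measurements, taken by blinded examiners at all three visits.

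**The concern.** There are two linked problems.

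**Order of readings.** By the time plaque is judged, an instrument has passed along the margin and some sites are bleeding. Blood could hide plaque, or could be taken for it. Blinding to arm does not prevent this, because the examiner still sees the blood. Bleeding and/or suppuration is a diagnostic criterion at entry (section 3.3), and the bleeding endpoint is a 50-60% reduction (section 2.2). An error tied to bleeding would therefore not be constant over time. Section 5.1 hypothesises a larger fall in bleeding with aPDT, so if the treatment works, the error would differ by arm as well.

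**Label.** Calling plaque an improvement produced by less inflammation reverses the direction given in section 1.1. All patients also receive prophylaxis or maintenance and hygiene instruction (section 6.3b), so plaque at weeks 6 and 12 partly reflects home care. Section 11.2c applies mixed models to data sets that it does not name, with a binomial option. A plaque result could thus be reported as efficacy without ever having been declared an outcome.

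At stake are the reading of the plaque score and its use as a check that hygiene stayed comparable between arms. Bleeding on probing (BOP) and probing depth (PPD) are not at stake.

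**Working it through.** The plan gives no figure that depends on this order, so there is nothing to reproduce. The only documented number used is 32 patients per arm (section 3.1) with six sites each (section 6.3b). All plaque, bleeding and error rates below are assumptions.

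**Model.** Let p be the true share of sites with plaque, b the share that bleed, m the chance that plaque is missed at a bleeding site, and g the chance that a clean bleeding site is scored as plaque.

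Recorded plaque = p(1 − b·m) + (1 − p)·b·g

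**1. Arm comparison.** Take the same p in both arms. Then test minus control = (b_control − b_test) × [p·m − (1 − p)·g].

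- Equal bleeding: the first factor is 0, so the false difference is 0.
- Blood hides plaque (g = 0), with p 30-70%, m 10-30% and 20 to 40 points less bleeding on aPDT: from 0.20 × 0.30 × 0.10 = 0.6 points to 0.40 × 0.70 × 0.30 = 8.4 points **more** recorded plaque on aPDT.
- Blood is read as plaque (m = 0), with g 10-30%: from 0.20 × 0.30 × 0.10 = 0.6 points (p = 70%) to 0.40 × 0.70 × 0.30 = 8.4 points (p = 30%) **less** recorded plaque on aPDT.

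The size varies fourteen-fold and the sign reverses.

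**2. Change over time.** Assume that true plaque falls from 60% to 40% in both arms, and that bleeding is 80% at baseline and 45% (control) or 25% (test) at week 12. The true fall is 20 points.

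| Error | Baseline | Week 12 control | Week 12 test | Fall, control | Fall, test |
|---|---|---|---|---|---|
| m = 0.1 | 55.2 | 38.2 | 39.0 | 17.0 | 16.2 |
| m = 0.3 | 45.6 | 34.6 | 37.0 | 11.0 | 8.6 |
| g = 0.1 | 63.2 | 42.7 | 41.5 | 20.5 | 21.7 |
| g = 0.3 | 69.6 | 48.1 | 44.5 | 21.5 | 25.1 |

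Examples: 60 × (1 − 0.8 × 0.1) = 55.2, and 60 + 40 × 0.8 × 0.1 = 63.2.

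If blood hides plaque, the fall is under-recorded by 3.0 to 11.4 points, with a false arm difference of 0.8 to 2.4 points against aPDT. If blood is read as plaque, the fall is over-recorded by 0.5 to 5.1 points, with a false difference of 1.2 to 3.6 points in favour of aPDT. The control column shows that change over time would be affected even if both arms bled equally.

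**3. Scale.** Sites per arm: 32 × 6 = 192. At 40% plaque, the standard error of an arm difference, ignoring clustering, is √(2 × 0.4 × 0.6 / 192) = 5.0 points. A false difference of 0.8 to 2.4 points is 1.5 to 4.6 sites, under half a standard error. At the extreme of step 1, 8.4 points against √(2 × 0.7 × 0.3 / 192) = 4.7 points is about 1.8 standard errors. Clustering of sites within patients enlarges the standard errors, so these ratios are upper limits.

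**The case against.** The strongest reply is that a scoring error is only a possibility. The documents report no error rate for plaque judged after probing. The order is the same in both arms, the examiners are blinded, and no arm difference arises unless the arms bleed differently. Dislodgement by the probe could occur at any swept site, bleeding or not, so it gives no reason for the error to follow bleeding; only masking or misreading by blood does that. The sweep is also gentle and stays just inside the sulcus, so its overlap with the surface scored for plaque is unknown. Hygiene instruction goes to everyone and does not by itself bias a randomised comparison. All of this stands, and it keeps the point minor.

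A reader might go further and infer that the plaque result **is** distorted by bleeding and so cannot be evidence for aPDT. The documents do not support that. If blood hides plaque, the bias runs against aPDT, so an observed plaque benefit would be understated rather than false. If blood is read as plaque, the bias runs the other way. The case against using plaque as an efficacy result rests on the causal label and the absence of a declared plaque outcome, not on the order of readings.

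The reply does not remove two facts: section 6.3b fixes the order, and it says plaque will be analysed as an improvement due to less inflammation. Equal bleeding between arms protects the arm comparison only, not the change from baseline.

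**Conclusion.** The point holds as a minor one. The order of readings leaves the plaque score open to an error from the sweep or from blood. If that error depends on bleeding, it would differ between visits, and between arms if aPDT reduces bleeding. The illustrative 0.6 to 8.4 points rests wholly on assumed plaque, bleeding and error rates; the documents fix neither size nor sign. The label is a documented inconsistency: section 6.3b presents plaque as a consequence of reduced inflammation, while section 1.1 presents biofilm as its cause. No hypothesis and no primary or secondary outcome rests on the plaque score, and the BOP and PPD results are not affected.

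**What to change.** In section 6.3b, at baseline, week 6 and week 12, score presence or absence of plaque at the six sites before the bleeding sweep. Leave the timing of plaque sampling as it is, at baseline and week 12 only; the change must not be worded so that it adds a week-6 sample.

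In the same paragraph, take plaque out of the list of improvements attributed to reduced inflammation. State that it will be reported by arm and visit as a descriptive check on hygiene.

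The cost is a swapped order of two existing readings and a small wording change, with no added visit, test or staff time. The downside is that plaque can no longer be cited as an efficacy result.

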7. TRIAL MATERIALS

7.1 Trial Products

Diode laser (660nm) will be used in conjunction with methylene blue photosensitizing dye. Antimicrobial photodynamic therapy uses low level laser light and aims to destroy pathogens around the implant and can also act as a photobiomodulator reducing inflammation and stimulating cellular proliferation (Mizutani et al. 2016). Antimicrobial photodynamic therapy works through an interaction between the photosensitizer (methylene blue or toluidine blue), red light (625–740 nm), and oxygen. The methylene

blue dye is taken up by the bacteria and the visible red light excites the dye. Excited dye transfers energy to tissue oxygen forming a singlet oxygen molecule. Singlet oxygen is highly reactive and will affect the bacterial cell by damaging the cell membrane and cell wall. The bactericidal effect is through DNA damage and more importantly damage to the cytoplasmic membrane (Takasaki et al. 2009). To activate the photosensitizer, the laser light can be delivered via a fiber placed into the pocket or transmitted through the mucosa. Saffarpur et al. (2018) through an in vitro study evaluated implants treated with aPDT and found no change in the implant surface. Neither the dye nor the low-level energy laser changed the implant surface characteristics. aPDT applied to rough titanium or zirconia surfaces have maintained the surface integrity of the treated implants. (Azizi et al. 2018, Giannelli et al. 2017). The photosensitizer, such as methylene blue, undergoes a strong cationic charge, which can bind to the outermost membrane of gram-negative bacteria and can penetrate bacterial cells. This creates selectivity of the dye to affect bacterial cells rather than human tissue cells (Takasaki et al. 2009). Also, the singlet oxygen molecule has a short lifetime and limited migration, so the reaction and cellular damage is contained within a limited space (Takasaki et al. 2009).

8. TREATMENT

8.1 Rationale for selection of treatment

Managing peri-implant disease with adjuncts like antiseptics and systemic antibiotics has a few disadvantages. Systemic antibiotic usage can produce antimicrobial resistance. Conventional mechanical debridement of the implant surface is limited by the contaminated microstructure of the implant surface. Bacteria might be protected by hiding in micro-irregularities of the titanium implant surface. Antimicrobial photodynamic therapy may resolve some of difficulties of conventional antimicrobial and mechanical therapy and can work as an adjunctive to conventional mechanical treatment. The advantages of aPDT are its wide antimicrobial activity, can be applied multiple times without creating antibiotics resistance, and easier topical delivery reaching the micro-irregularities of the implant surface. Multiple in vitro studies have shown the antimicrobial properties of aPDT on various titanium surfaced seeded with periodontopathic microbes (Haas, Azizi, Huang, Marotti).

8.2 Specific Restrictions/ Requirements

No post operative restrictions or requirements are required after treatment. Oral hygiene instructions will be reviewed with patients after treatment including instruction on brushing and flossing.

8.3 Blinding

The investigator performing the treatment cannot be blinded because they will know if the dye has been applied and if the laser has been activated. Patient will be blinded because the control group will use a sham procedure including the use of saline and non-light emitting laser. The examiners will be blinded. The patients will be informed of benefits of all the procedures and realize that a minimum they are receiving the gold standard of peri-implant treatment, mechanical debridement.

9. SAFETY MEASUREMENTS

9.1 Definitions

All unanticipated problems will be reported in this study. The Committee for the Protection of Human Subjects (CPHS) considers unanticipated problems to be any incident, experience, or outcome that meets all of the following criteria:

- Is unexpected in terms of nature, severity, or frequency given a) the research procedures that are described in the IRB-approved research protocol and informed consent, and b) the characteristics of the subject population being studied;
- Is related or possibly related to participation in the research (possibly related means there is a reasonable possibility that the incident, experience, or outcome may have been caused by the procedures involved in the research); and
- Places subjects or others at a greater risk for physical, psychological, economic, or social harm than was previously known or recognized.
- An incident, experience, or outcome that meets the 3 criteria above will generally warrant consideration of substantive changes in order to protect the safety, welfare, or rights of subjects or others. Examples of corrective actions or substantive changes that might need to be considered in response to an unanticipated problem include the following:
- Changes to the research protocol initiated by the investigator prior to obtaining IRB approval to eliminate apparent immediate hazards to subjects
- Modification of inclusion or exclusion criteria to mitigate newly identified risks
- Implementation of additional procedures for monitoring subjects
- Suspension of enrollment of new subjects
- Suspension of research procedures in currently enrolled subjects

For this study, a severe adverse event (SAE) is defined as an unanticipated problem occurring during the study that fulfills 1 or more of the following criteria:

1. Results in death
2. Is immediately life-threatening[†]
3. Requires inpatient hospitalization or prolongation of existing hospitalization
4. Results in persistent or significant disability or incapacity
5. Is a congenital abnormality or birth defect
6. Is an important medical event that may jeopardize the subject or may require medical intervention to prevent one of the outcomes listed above

Hospitalization for elective procedures or surgeries will not be considered SAEs, nor will inpatient hospitalizations for convenience.

Pregnancy in women with childbearing potential should not be reported as an SAE, but if pregnancy occurs, it must be reported in accordance with the procedures described in Section 6.2. Pregnancy will not be regarded as an SAE unless there is suspicion that a study intervention may have interfered with the effectiveness of a contraceptive medication and the event meets the criteria for an unanticipated problem. If the pregnancy results in an outcome other than a normal birth or elective abortion of a healthy fetus, it will be reported as an SAE.

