9.2 Collecting, Recording and Reporting of Adverse Events

Examination and close follow-up of parameters capturing subjects' oral health will be collected on case report forms (CRFs). These will be completed at every study visit, and data will be compiled into a pre-specified format and reviewed monthly by the PI for safety oversight. Serious adverse events (as defined in Section 9.1) will be collected from the time of enrollment until the last clinic visit and will be recorded in the electronic health records (EHR) system. At each study visit, the clinician or investigator will inquire

about the occurrence of SAEs since the last assessment. The investigator will review all source documentation related to study procedures for evidence of SAEs. Events will be followed for outcome information until they return to baseline or stabilize, or until 30 days after study completion or subject discontinuation. Subjects who have an SAE that is ongoing 30 days after study completion or discontinuation will be referred to an appropriate practitioner for continued care. Upon learning that a subject has experienced an SAE, the investigator must report the event to CPHS within 24 hours after becoming aware of the event.

On a monthly basis, the following events will be reported to every PI:

- Number of subjects experience severe complications and number of subjects enrolled. Severe complications include severe pain, continuous bleeding and severe swelling that needs prescription to control.
- Duration of observation of subjects experiencing severe complications and duration of observation of subjects enrolled.
- Any tooth loss, abscess, or other adverse oral health development requiring therapy or other intervention and the etiology (as captured in the dental history)
- Every PI will review the monthly reports for any safety signals.

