11.2 Statistical and Analytical Plans

a. General Consideration

We will present means and standard deviations for completeness of the report. The statistical significance level to test the primary endpoint was set at $p<0.05$.

b. Safety Analyses

Safety will be evaluated by tabulations of adverse events and will be presented with descriptive statistics at baseline and follow-up visits each month.

Adverse events will be classified as severe complications and summarized for baseline and follow-up visits.

All information pertaining to adverse events noted during the study will be listed by subject, detailing verbatim given by the investigator, preferred term, date of onset, date of resolution, severity, and relationship to procedure. The onset of adverse events will also be shown relative (in number of days) to the day of performing the surgery.

c. Statistical Analysis Plan

We will analyze these data sets using generalized linear mixed effects models with the appropriate error structure (e.g., binomial, poisson) and specifying treatment (control mechanical debridement vs mechanical debridement + aPDT) as a fixed factor and repeated measures of individuals over 0, 6, and 12 weeks as a random factor. Demographic data collected from patients will be included in analysis and will be adjusted for any confounders. All quantitative analyses will be performed in R Statistical Software (R Core Team 2017).

For microbiologic analysis, microbial DNA will be purified using the QIAmp DNA Mini Kit (Qiagen, Hilden, Germany) or Qiagen DNA MiniAmp kit (Qiagen, Valencia, CA, USA), according to the manufacturer's protocol. 16S rRNA gene V4 amplification and sequencing will be completed. 16S rRNA gene data analysis will also be completed for the plaque samples.

For immunologic analysis, the PerioPaper strips will be analyzed using multiplexed fluorescent bead-based immunoassay. Assessments will be made in triplicate, and for the statistical analysis, median of the replicates will be used.

12. Ethical Consideration

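### The SAE definition requires an event to be unexpected and possibly related as well as serious, and the only stated visit enquiry covers SAEs although adverse events in general are to be tabulated

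*Combined protocol and SAP*

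**What the plan says.** Section 9.1 starts from the IRB's category of unanticipated problem, which is "any incident, experience, or outcome that meets all of the following criteria". There are three criteria. The first begins "Is unexpected in terms of nature, severity, or frequency given" and refers to the procedures described and the population studied. The second begins "Is related or possibly related to participation in the research". The third is that the event exposes subjects or others to more harm than was previously recognized.

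The section then builds the SAE on that category: "a severe adverse event (SAE) is defined as an unanticipated problem occurring during the study that fulfills 1 or more of the following criteria". Six seriousness criteria follow, running from death to important medical events.

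Section 9.2 collects serious adverse events by explicit reference to the 9.1 definition. At each visit the clinician or investigator asks "about the occurrence of SAEs since the last assessment". Source-document review and the 24-hour report to CPHS use the same term. A separate monthly report covers severe complications and oral events that need treatment.

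Section 11.2b plans tabulations of adverse events and a by-subject listing whose fields include "date of onset, date of resolution, severity, and relationship to procedure".

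Section 2.4b names the study risks as "Initial mild pain, swelling, and bleeding related to non-surgical implant surface mechanical debridement", together with reversible dye staining of the gingiva.

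**The concern.** Seriousness, expectedness and relatedness are three separate attributes of an event. Normally the event is captured first and the other two are recorded afterwards. Here they act as an entry condition: someone must judge an event unexpected and possibly related before it can be an SAE at all. If that judgement later proves wrong, there may be no record to re-examine, and events that were never collected cannot be recovered at analysis.

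There is also a mismatch between collection and analysis. Section 11.2b tabulates adverse events with severity and relationship, but the protocol gives no general definition of an adverse event and no general enquiry to feed those tables. The events most likely to occur are the mild ones in 2.4b. One of them, dye staining, can arise only in the aPDT arm, because the control arm receives saline.

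**Working it through.** No arithmetic applies, because the point rests on definitions and collection rules. The check follows each kind of event through the routes the protocol provides.

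**Step 1: the condition for an SAE.** Combining the two definitions in 9.1:

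SAE = unexpected AND at least possibly related AND greater risk than known AND at least one of six seriousness criteria.

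Failing any of the first three is enough to remove the label, however serious the event.

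**Step 2: where the condition is used.** Because 9.2 points to 9.1, the same condition governs collection, the visit enquiry, source review and the 24-hour CPHS report.

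**Step 3: events against routes.**

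| Event | SAE (9.1), so visit enquiry and 24-hour report (9.2) | Monthly report (9.2) | Listing (11.2b) |
|---|---|---|---|
| Death or hospitalization, non-oral, judged unrelated or expected | No | No | Only if noted |
| Severe pain, bleeding or swelling needing a prescription | Only if all conditions in step 1 hold | Yes, with no relatedness or expectedness test | If noted |
| Tooth loss, abscess or other oral event needing intervention | Only if all conditions in step 1 hold | Yes, with etiology and no relatedness test | If noted |
| Abnormal pregnancy outcome | Yes, by a separate rule in 9.1 | Not named | If noted |
| Mild pain, swelling, bleeding or dye staining | No | No | Only if noted |

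The first and last rows are the gaps. The two middle oral rows are covered by the monthly report whether or not they qualify as SAEs.

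**Step 4: consistency of the term.**
- Section 6.3e gives life-threatening disease and hospitalization as examples of a serious adverse event, with no unanticipated-problem condition.
- The pregnancy paragraph in 9.1 makes an abnormal outcome an SAE without that condition, although its preceding sentence applies the condition to pregnancy itself.
- Section 9.1 calls the category severe, while 9.2 calls it serious and cites 9.1.
- Section 11.2b says adverse events are to be classified as severe complications, which leaves milder events without a category.

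**The case against.** The strongest reply is that the protocol has more safety routes than the SAE definition, and that stronger readings of this point go too far. Much of that stands.

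- A reader might infer that expected or unrelated serious events are never counted anywhere. The documents do not support that. The monthly report takes in severe complications and treated oral events with no test of relatedness or expectedness, abnormal pregnancy outcomes are SAEs in their own right, and 11.2b lists any adverse event that is noted. The accurate statement is that such events are not counted as SAEs.
- A reader might infer that a serious bleed is excluded as expected because 2.4b lists bleeding. Section 2.4b lists mild events only, and criterion 1 covers unexpected severity, so a serious bleed could well qualify.
- A reader might infer that an unblinded investigator applies the filter. The treating investigator is unblinded and the examiners are blinded, but no section says who judges relatedness or expectedness. An unblinded judgement is possible, not established.
- A reader might infer that a planned between-arm safety test is biased. Section 11.2b plans tabulations, descriptive statistics and listings, and specifies no comparison by arm.
- A reader might infer that 11.2b promises to list every adverse event. It lists those noted. Its relationship field also refers to the procedure, whereas 9.1 refers to participation in the research, so the field still carries some information for SAEs.

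It is also fair to say that CRFs record oral-health parameters at every visit. The data collection form is listed as Appendix 1, but its content is not shown, so it may contain adverse event fields that cannot be assessed here.

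None of this covers the serious non-oral event judged unrelated or expected, or supplies a stated question for mild events. Section 6.3e might be read as shorthand for the 9.1 definition, but its wording does not say so.

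**Conclusion.** The point holds in this form. The 9.1 definition merges seriousness with expectedness and relatedness, and 9.2 carries that into collection, enquiry and expedited reporting. Serious non-oral events judged unrelated or expected have no dedicated route, and mild events named as study risks have no stated enquiry. The wording also disagrees with 6.3e and with the pregnancy rule in 9.1.

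The size cannot be put as a number, because the documents give no rate for serious or mild events. The setting is 74 recruited patients, a topical dye and low-level laser applied at one treatment visit, and 12 weeks of follow-up, so few SAEs may occur. The BOP and PPD outcomes and their analysis are not affected. This is a correction that should be made, but it does not put the trial's main conclusion at risk.

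The conclusion assumes that staff apply 9.1 and 9.2 as written, and that Appendix 1 does not already contain a general adverse event enquiry. If it does, the gap for mild events narrows, but the definitional problem remains.

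**What to change.** 1. In 9.1, define an SAE by the six seriousness criteria alone, and use one term (serious) throughout.
2. Keep unanticipated problem as a separate category for CPHS reporting, with its three criteria unchanged.
3. In 9.2, add an open question about any adverse event at the 6-week and 12-week visits. Record seriousness, severity, relatedness and expectedness as attributes of each event, and state who assigns them.
4. In 11.2b, tabulate what is then collected, with categories for events below the severe-complication level.
5. Reconcile 6.3e, 9.1 (including the pregnancy paragraph), 9.2 and 11.2b so that the same definition applies in each.

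The cost is protocol wording, its IRB review as an amendment, and slightly more event recording. For 74 patients and two existing follow-up visits, the open question is asked at most 74 × 2 = 148 times, before any replacement of withdrawn subjects. No extra visit is needed.
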